15.7.2 Duration of response

The DOR defined as time from improved baseline tumor assessment achieved on study drug (CR and/or PR) to worsening will be estimated and summarized by descriptive statistics and listed.

15.7.3 Progression-Free Survival

Progression-free survival will be estimated only for the overall cohort. Patients with no event will be censored at their study discontinuation visit, including study completion. Kaplan-Meier estimates for the 25%, median and 75% quartiles with respective 95% confidence intervals will be presented and graphically displayed. The safety set will be used. All data will be listed.

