8.2 Secondary Objectives

Secondary objectives are to:

1. Evaluate the safety and toxicity of AFM13
2. Determine the clinical efficacy, namely objective response rate (ORR), [including complete response (CR) and partial response (PR)], duration of response (DOR) and progression-free survival (PFS) as defined in the Revised Response Criteria for Malignant Lymphoma 2007 and modified Severity-Weighted Assessment Tool (mSWAT)
3. Evaluate the pharmacokinetic profile (PK) of AFM13.

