10.7 End of Study Visit

Subjects will return to the study site for an EoS visit after the last treatment or during week 11. At this visit the following will be performed:

- physical examination
- vital signs
- 12-lead ECG
- Optional skin biopsy, if requested by the investigator and agreed upon by the patient
- concomitant medication
- blood sampling for the following:
 - clinical chemistry, hematology and coagulation
 - blood for immunology
 - sCD30
 - ADAs

Patients who discontinue the study for any reason should undergo EoS assessments, if at all possible.

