10.13 Withdrawal of Patients

Subjects have the right to withdraw from the study at any time and for any reason without prejudice to future medical care by the physician or at the institution.

Any subject who withdraws consent to participate in the study will be removed from treatment and/or study observation immediately upon the date of request. All subjects who withdraw from treatment prematurely before completion of the protocol-specified tests and procedures are strongly encouraged to complete the safety follow-up visit.

If a patient's participation is terminated prematurely, the cause for the early termination and the date and time of the termination will be documented in the patient's case report form (CRF) and in the final Clinical Study Report (CSR).

Patients will be withdrawn from treatment for the following reasons:

1. Disease progression
2. Unacceptable toxicity, as defined by the CTCAE Version 4 and in the determination of the Principal Investigator
3. Withdrawal of consent
4. General or specific changes in the patient's condition that render the patient unacceptable for further treatment in the judgment of the investigator

Female patients of childbearing potential will be asked to adhere to the requirements of not becoming pregnant and using an acceptable method of contraception as specified in Section 0.

If a patient withdraws or is dismissed from the study, all procedures planned for the EoS visit (Section 10.7) will be completed, where possible. If a patient is withdrawn or dismissed from the study, all ongoing AEs should be followed up for 30 days after the last administration of study drug, with the exception of any ongoing study drug-related AEs, which should be followed until resolution or stabilization (if in the investigator's opinion, the AE is unlikely to resolve due to the patient's underlying disease).

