12.6 Management of Other AFM13-related Side Effects

The management of other AFM13-related AEs is described in Table 5. If a patient presents with symptoms indicative for nasopharyngitis or pneumonia, samples for microbiological diagnostics should be obtained. The patient should be admitted to hospital and an empirical antibiotic treatment should be immediately started in the case of pneumonia or if the infection is associated with a significant impairment of the general condition.

Continuous safety analyses (AEs, safety clinical laboratory assessments, vital signs, ECGs) will be regularly performed by a Principal Investigator-led safety team to ensure the safety of the patients. In the case of a potential significant safety problem the Principal Investigator in consultation with groups such as the FDA, IRB, data monitoring committee and/or statisticians may decide on the termination or temporary cessation of the trial.

Table 5: Management of Other AFM13-associated Adverse Events

CTCAE grade	Management of other AFM13-associated AEs
Grade 1	Symptomatic treatment as applicable
Grade 2 or 3	Interruption of AFM13 infusion if event develops during infusion; symptomatic treatment as applicable Delay next AFM13 dose until the AE has recovered to CTCAE Grade 0 or 1; if delay was more than 21 days, permanently discontinue AFM13 treatment Exception: in the case of documentation of a CTCAE Grade 2 or 3, non-clinically significant, laboratory value or non-clinically significant AE e.g. Grade 2 fatigue, the treatment can be continued under close monitoring of the laboratory changes (suggest two-day intervals)
Grade 4	Permanent discontinuation of AFM13, symptomatic treatment as applicable

AE=adverse event, CTCAE=Common Terminology Criteria for Adverse Events

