12.8 Treatment Schedule Interruptions (Delayed or Skipped Doses)

The treatment with AFM13 should be interrupted, if an AE occurs according to Table 4 and 5. Any skipped dose will not be made up. If there is a delayed of more than 3 weeks, the patient will be removed from study.

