12.9 Study Drug Discontinuation

The study drug must be discontinued if a drug-related CTCAE Grade 4 AE occurs at any time. Patients who discontinue study drug should be scheduled for an end-of-treatment (EoT) visit one week after the last dose of study drug, at which time all of the assessments listed for the EoS visit (Section 10.7) will be performed. A form should be completed, giving the date and reason for stopping the study drug. It is recommended to have these patients return for the Restaging Visit on what would have been their Week 11 of that cycle after the last AFM13 dose for post-treatment safety evaluations, for tumor assessments and restaging (Section 10.6). If a new therapy is planned to be started before Week 11, the final restaging visit should be performed before administration of this therapy.

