13.3 Definitions

Evaluable for objective response. Patients who complete 1 cycle of therapy according to the study protocol, and have had their disease re-evaluated will be considered evaluable for response. When no imaging/measurement is done at all at a particular time point, the patient is not evaluable at that time point. Similarly, patients whose tumour assessments are not repeated/incomplete will also be considered non evaluable for response. Patients evaluable for response will have their response classified according to the definitions stated below. Patients who exhibit objective disease progression prior to the end of Cycle 1 will also be considered.

Table 6: Global Response Score

Global Score*	Definition	Skin	Nodes/Blood/Viscera
CR	Complete disappearance of all clinical evidence of disease	CR	All categories have CR/NI
PR	Regression of measurable disease	CR	All categories do not have a CR/NI and no category has a PD
		PR	No category has a PD and if any category involved at baseline, at least one has a CR or PR
SD	Failure to attain CR, PR, or PD representative of all disease	PR	No category has a PD and if any category involved at baseline, no CR or PR in any
		SD	CR/NI, PR, SD in any category and no category has a PD
PD	Progressive disease	PD	PD in any category
Relapse	Recurrence disease in prior CR		Relapse in any category

CR=complete response; NI=noninvolved; PD=progressive disease; PR=partial response; SD=stable disease

*It is recommended that not only the proportion of patients who achieve a response or an unfavorable outcome be calculated but a life table account for the length of the interval during which each patient is under observation also be generated.

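### PFS censoring in 15.7.3 is tied to a discontinuation visit with no mSWAT, CT or PET, so some early leavers can be credited with time beyond their last formal tumour assessment

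*Combined protocol and SAP*

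**What the plan says.** Section 15.7.3 estimates PFS by Kaplan-Meier for the overall cohort in the safety set, with this censoring rule: "Patients with no event will be censored at their study discontinuation visit, including study completion". Section 8.2 defines PFS by the 2007 revised lymphoma criteria and mSWAT.

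The 10.7 list for the end-of-study (EoS) visit contains a physical examination, vital signs, ECG, an optional biopsy, concomitant medication and blood samples. It has no mSWAT, CT or PET. The list also applies to people who leave: "Patients who discontinue the study for any reason should undergo EoS assessments, if at all possible" (10.7) and "If a patient withdraws or is dismissed from the study, all procedures planned for the EoS visit (Section 10.7) will be completed, where possible" (10.13).

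Formal tumour assessment is scheduled at Week 11 of each cycle (10.5, 10.6), and the Table 2 notes allow 2 weeks either side. For objective response, 13.3 says: "When no imaging/measurement is done at all at a particular time point, the patient is not evaluable at that time point". Section 15.7.3 has no counterpart for PFS.

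Three other sections bear on early leavers:
- **12.8:** "If there is a delayed of more than 3 weeks, the patient will be removed from study". For the same delay, Table 5 in 12.6 says only "if delay was more than 21 days, permanently discontinue AFM13 treatment".
- **12.9**, for patients who stop drug: "It is recommended to have these patients return for the Restaging Visit" at what would have been Week 11, with restaging brought forward if new therapy starts sooner.
- **10.5:** after serious, persistent Grade 3 or 4 toxicity that stops treatment, response should be assessed within 4 weeks of the last dose.

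**The concern.** A PFS time says that a patient was free of progression up to a given date, by the criteria that define progression. Here the censoring date is a visit at which those criteria need not be applied. Someone who leaves before Week 11 may have no formal assessment after baseline, yet contributes progression-free time up to the discontinuation visit. That time keeps the patient in the risk set and can hold the curve up.

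Section 12.8 makes such departures somewhat more likely. It takes the patient off study where Table 5 only stops the drug, and leaves unclear whether the 12.9 recommendation still applies. It does not cause the problem: the censoring rule would have this property for any off-schedule departure.

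**Working it through.** The plan states no PFS figure, so there is none to reproduce. Time is counted from Day 1 of Cycle 1; this is an assumption, as 15.7.3 names no origin. The Cycle 2 columns of Table 2 cannot be read reliably in the text version, and tumour assessment there may fall under EoS/PD, so the timing is worked for Cycle 1 only.

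**1. When 12.8 can remove a patient.** Inputs: weekly dosing (Table 1), a delay of more than 21 days (12.8, Table 5), Week 11 visit, window of 2 weeks either side (Table 2 notes).
- Due day of dose k = 7k − 6.
- First day with a delay over 21 days = due day + 22.
- Week 11 Day 1 = 7 × 11 − 6 = Day 71; the window opens on 71 − 14 = Day 57.

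| Dose | Due day | Trigger day | Days before Day 71 | Days credited from Day 1 |
|---|---|---|---|---|
| 2 | 8 | 30 | 41 | 29 |
| 3 | 15 | 37 | 34 | 36 |
| 4 | 22 | 44 | 27 | 43 |
| 5 | 29 | 51 | 20 | 50 |
| 6 | 36 | 58 | 13 | 57 |
| 7 | 43 | 65 | 6 | 64 |

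The last column assumes no restaging and a discontinuation visit on the trigger day; censoring at the last assessment would credit 0. Dose 8 (due Day 50) triggers on Day 72, after the Week 11 visit. If delay runs from the last dose, the trigger is due day + 15, and doses 2 to 8 give 22 to 64 days.

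**2. Direction.** Each Kaplan-Meier factor is 1 − d/n. With the same event dates, later censoring leaves d unchanged and n equal or larger, so every factor is equal or larger. The curve under 15.7.3 is therefore never lower than under last-assessment censoring.

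**3. When the curves differ.** They differ only if another patient's event time is later than the affected patient's last assessment and no later than that patient's discontinuation visit. If progressions are recorded at Week 11 (Day 71), every trigger day in the table comes earlier and the two curves are identical. For doses 2 to 5 this holds even for events on Day 57. A difference needs an earlier clinical progression (13.3 allows for progression before the end of Cycle 1), restaging early in the window against a dose 6 or 7 removal, or a discontinuation visit later than the trigger day.

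**4. Size when they do differ.** The number affected, m of 15, is assumed. For a first progression recorded before the affected patients' visits, the drop is 1/15 = 6.67% under 15.7.3 and 1/(15 − m) under last-assessment censoring:
- m = 1: 1/14 = 7.14%, a difference of 0.48 points
- m = 2: 1/13 = 7.69%, a difference of 1.03 points
- m = 3: 1/12 = 8.33%, a difference of 1.67 points

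**5. A less favourable assumed case.** Six progressions are found at Week 11, and m event-free patients have no assessment after baseline and a discontinuation visit in Week 12. Survival just after Week 11 is 1 − 6/15 = 0.600 under 15.7.3. Under last-assessment censoring it is 1 − 6/14 = 0.571 for m = 1 and 1 − 6/12 = 0.500 for m = 3, where the median moves from not reached to 11 weeks. With the discontinuation visit in Week 8 instead, both rules give the same curve. Week 12 is later than every trigger day in step 1, so this shows sensitivity and is not an expected size.

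**The case against.** The strongest reply is that the rule rarely matters. Formal assessment happens at Week 11, most 12.8 removals come earlier, and those patients leave the risk set before the first scheduled event under either rule. That stands. A reader might take the 29 to 64 credited days as a measure of inflated PFS; step 3 shows that they usually do not alter the curve.

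The reply also has force on coverage. Sections 9.6 and 10.7 allow the EoS visit at Week 11, when 10.5 and 10.6 call for mSWAT and imaging, so completers seen then have no gap. It would be wrong to infer that all event-free patients are affected. Where 10.5 applies, the last dose precedes the missed one by 7 days and removal follows the due date by 22, so removal falls 29 days after the last dose. The assessment due within 28 days should then come first. Persistent Grade 2 events, which Table 5 includes, fall outside that safeguard, and 12.9 only recommends restaging.

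Nor is the time unobserved. Physical examination is marked at every weekly visit and at EoS, covers skin, nodes, spleen and liver (14.16), and is named as a response tool in 13.2. But it is not mSWAT or imaging, and the Table 2 notes make interim examinations symptom-directed and as needed.

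Last-assessment censoring also has a weakness: it counts progressions found off schedule while discarding off-schedule observation without progression. It is a convention, not a guarantee of less bias. Finally, 15.1 promises an SAP before database lock that may refine the rule; 15.7.3 is the rule that can be read now.

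**Conclusion.** The point holds as a minor one. Section 15.7.3 can credit progression-free time past the last formal tumour assessment for patients who leave outside the Week 11 restaging and are not caught by 10.5 or 12.9. Relative to last-assessment censoring, the curve is equal or higher. For Cycle 1 removals before Week 11 the difference is often nil and otherwise small: 0.5 to 1.7 points on a first early step if one to three of 15 patients are affected. That number is an assumption; the documents give none.

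A reader might infer that reported PFS will be biased upward against the true PFS. The documents do not support this: removal after toxicity may be related to outcome in either direction, so the size and sign of that bias are unknown. Nor does anything here touch ORR or the primary biological endpoint. PFS is secondary and descriptive, with no test or decision attached.

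**What to change.** In 15.7.3, censor event-free patients at the date of the last adequate tumour assessment, or at Day 1 if there is none after baseline. This is a wording change and needs no extra procedure. Its cost is that some PFS times become shorter, down to 0 days where nothing was assessed after baseline, so early Kaplan-Meier steps rest on fewer patients.

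An optional supporting edit is to align 12.8 with Table 5: after a delay of more than 3 weeks, stop AFM13 permanently and follow the patient under 12.9. Making the 12.9 restaging expected instead of recommended would help recover outcomes, at the price of firming up a visit already suggested. The censoring change does not depend on either.

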15.7.4 Pharmacokinetics

A descriptive PK analysis will be conducted, Mean, standard deviation, median and range will be calculated for continues measurements, frequency and percentages for categorical data. Only patients in the safety set that have a respective baseline and at least one post-baseline measurement will be used

15.8 Safety Objectives

15.8.1 Adverse Events

All AEs recorded during the study will be coded by MedDRA (Medical Dictionary for Regulatory Activities). The incidence of AEs will be summarized by cohort, overall, primary system organ class, preferred terms and severity based on CTCAE version 4.0. Relationship to study drug, AEs leading to discontinuation of study drug, death and SAEs, will be summarized.

Infusion-related AEs will be summarized by preferred term and severity. A list of AEs related to skin disease using pre-defined MedDRA preferred terms will be used to identify any AEs of special interest. All AEs will be listed. The safety set will be used.

15.8.2 Laboratory Abnormalities

Laboratory values and severity grades will be calculated using CTCAE version 4.0. For those parameters where there is no CTCAE grading defined a classification into lower limit, normal and higher limit will be used. Shift tables for change from baseline will be presented as well as descriptive statistics mean, standard deviation, median, and range for absolute values by visit and change from baseline will be summarized. All lab values, abnormalities will be listed. The safety set will be used.

15.8.3 Vital Signs

Vital signs will be summarized by mean, standard deviation, median and range for absolute values by visit and change from baseline. The number of abnormal vital signs will be summarized by visit. All values will be listed. The safety set will be used.

15.8.4 Other Safety Parameters

All other safety parameters such as ECG will be listed for the safety set.

15.9 Exploratory Objectives

15.9.1 Presence of Anti-AFM13 Antibody

The presence of anti-AFM13 antibodies and their neutralizing function will be assessed by descriptive statistics (mean, standard deviation, median and range). The safety set will be used. All data will be listed.

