4 STUDY SYNOPSIS

Sponsor: Columbia University Medical Center Center for Lymphoid Malignancies [name]
Title of Study: Clinical and Biological Evaluation of the Novel CD30/CD16A Tetravalent Bispecific Antibody (AFM13) in Relapsed or Refractory CD30-Positive Lymphoma with Cutaneous Presentation: A Biomarker Phase Ib/Ia Study
Phase: Ib/Ia
Principal Investigator: [name]
Name of Investigational Product: AFM13, Recombinant antibody construct against human CD30 and CD16A (TandAb®)
Study Center: Columbia University Medical Center, [name]
Publications: None.
Planned Study Period: Q3 2017 to Q4 2019 (first patient first visit to last patient last visit)
Objectives: The primary objectives are to: 
1. Determine the intratumoral NK-cell and T-cell infiltrate and density2. Determine the immunophenotype of immune cells (NK cells, T cells and others) in tumor and peripheral blood3. Quantitate the plasma cytokine production and release in tumor and peripheral blood as a function of treatment. Secondary objectives are to: 
1. Evaluate the safety and toxicity of AFM132. Determine the clinical efficacy, namely objective response rate (ORR), [including complete response (CR) and partial response (PR)], duration of response (DOR) and progression-free survival (PFS) as defined in the Revised Response Criteria for Malignant Lymphoma 2007 and modified Severity-Weighted Assessment Tool (mSWAT)3. Evaluate the pharmacokinetic profile (PK) of AFM13. Exploratory objectives are to: 
1. Determine the immunogenicity of AFM132. Detect and quantify circulating tumor cells (CTC).
Methodology: This is an open label, Phase Ib/Ia study designed to evaluate primarily the biological and immunological activity of AFM13 in tumor and blood when administered as monotherapy to patients with CD30-positive lymphomas with cutaneous presentation. Four cohorts of 3 patients will be treated with different doses of AFM13 and dose regimens.
Number of Patients: It is planned that at least 15 eligible patients will be accrued.
Diagnosis and Main Eligibility Criteria: This study will enroll patients with relapsed or refractory CD30-positive lymphoma with cutaneous presentation.

Sponsor:

Columbia University Medical Center
Center for Lymphoid Malignancies [name]

Inclusion criteria:

1. Age ≥ 18 years

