- Maximum measured plasma concentration (C_{max})

Other descriptive variables may be applied accordingly such as:

- Area under the curve (AUC)
- Distribution volume (VD)
- Terminal half-life (t^{1/2})
- Clearance

AFM13 immunogenicity (exploratory endpoint)

- Screen for presence of anti-drug antibodies (ADAs)
- Neutralizing potential of ADAs
- NK cell cytotoxicity against CD30-positive targets and cytotoxic T lymphocyte (CTLs) function

Statistical Methods:

Sponsor:

Columbia University Medical Center
Center for Lymphoid Malignancies [name]

As this is an exploratory study, no hypothesis will be tested and thus no formal sample size calculation has been undertaken. The response rate will be estimated and their respective exact 95% confidence intervals will be constructed based on Binomial distribution.

Based on the prior Phase 1 study of AFM13, it is expected that approximately 78% of the patients will show immunological and biological activity. Observing 12 patients out of 15 with immunological and biological response would lead to 95% exact binomial confidence interval of 52%-96% showing activity. The lower bound of 52% is assumed to be sufficient for evidence of activity in this exploratory study.

No formal interim analysis is planned, however a safety committee (not a formal data safety monitoring board) will review the safety data from each cohort and advise on opening the next cohort.

Version and date of the Protocol: 1.4 February 1st, 2019

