8.3 Exploratory Objectives

Exploratory objectives are to:

1. Determine the immunogenicity of AFM13
2. Detect and quantify circulating tumor cells (CTC).

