The biological and immunological studies will investigate the NK cell phenotypic characteristics, proliferative response (Ki-67), activation status (CD69), and density in the peripheral blood. The same analyses will be conducted in the tumor tissue collected from all patients at different time points. In addition, tumor cell infiltrate by NK cell and their spatial distribution in the tumor and its microenvironment will be studied. NK effector function will be assessed in both compartments (peripheral blood and tumor) by assaying for ADCC, presence of cytolytic proteins (granzyme B, perforin-1), and the production and release of cytokines and chemokines. T cells phenotype and effector function (CTL) will also be studied. Additionally, tumors obtained from study participants will be analyzed for expression of CD30, major histocompatibility antigens (MHC Class-I), other immune cell infiltrates, and resident immune cells (myeloid-derived suppressor cells, regulatory T cells (Tregs).

The presence of anti-AFM13 antibody will be investigated, and their neutralizing ability assayed.

Continuous safety analyses (AEs, safety clinical laboratory assessments, vital signs, ECGs) will be regularly performed by a Principal Investigator-led safety team to ensure the safety of

the patients. In the case of a potential significant safety problem the Principal Investigator in consultation with groups such as the FDA, IRB, data monitoring committee and/or statisticians may decide on the termination or temporary cessation of the trial.

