15 STATISTICAL EVALUATION

15.1 Statistical Methods

The data will be analyzed by the Columbia University Medical Center. This is a single center study. The data will be summarized with respect to demographic and baseline characteristics, biological activity measurements, safety observations, efficacy observations, PK and potential biomarker observations. The data will be presented by dose cohorts and overall. The clinical database lock will occur after all data are reconciled (i.e. “cleaned”) for all patients. A single clinical study report will be generated for this study. The Statistical Analysis Plan (SAP) will be finalized and signed before the database lock.

The data analysis will take place after the time of database lock when all patients have completed 2 cycles or discontinued the study prior and all data is cleaned. Further data for patients that are followed up past the two cycles will be summarized in an extension report once all patients have discontinued the study. All analyses are of exploratory nature.

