15.2 Sample Size and Power

The planned total target accrual for this study is 15 subjects.

As this study is of exploratory nature no formal sample size calculation is done. However based on the prior phase I study of AFM13, it is expected that approximately 78% of the patients will show biological activity. Observing 12 patients out of 15 with biological response would lead to 95% exact binomial confidence interval of (52%, 96%). The lower bound of 52% is assumed to be sufficient for evidence of biological activity in this exploratory study.

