15.4 Demographics, Baseline Characteristics and Medical History

Demographics, baseline characteristics and medical history will be analyzed for the safety set by cohort and overall. For continuous variables, descriptive statistics will be presented including: mean, standard deviation, median and range. For categorical variables frequency and percentages will be presented. All data will be listed.

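### Section 15.9.1 summarises ADA presence, a positive/negative result, by mean, SD, median and range, with no count, percentage or interval and no rule for patients lacking a post-baseline sample

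*Combined protocol and SAP*

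**What the plan says.** Immunogenicity is an exploratory objective (section 8.3: "Determine the immunogenicity of AFM13"). The synopsis describes the first part of the endpoint as "Screen for presence of anti-drug antibodies (ADAs") and adds the neutralising potential of those antibodies. Section 9.1 says: "The presence of anti-AFM13 antibody will be investigated, and their neutralizing ability assayed".

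The analysis is in section 15.9.1: "The presence of anti-AFM13 antibodies and their neutralizing function will be assessed by descriptive statistics (mean, standard deviation, median and range"). That section uses the safety set and promises a full listing. It gives no frequency, percentage or confidence interval.

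Elsewhere the plan treats categorical data differently. Section 15.4 states: "For categorical variables frequency and percentages will be presented". Sections 15.6 (primary endpoints) and 15.7.4 (PK) have the same provision. Each applies only within its own section, and section 15.1 has no general rule for categorical data that would reach ADA. Section 15.1 does set the level of presentation: "The data will be presented by dose cohorts and overall".

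**The concern.** Mean, SD, median and range are a template for continuous measurements. Whether a patient has anti-drug antibodies is positive or negative, and the natural summary is how many patients out of how many. Followed literally, 15.9.1 answers the immunogenicity objective with four statistics, of which only the mean carries the rate, and it plans no statement of uncertainty. The weakness is greatest at the result most likely to be quoted as reassuring, a count of zero.

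There is also a denominator question. Section 15.3 defines the safety set as everyone given at least one dose. ADA samples are taken before dosing on Week 1 Day 1, on Week 3 Day 1 and at the end-of-study visit (sections 10.3, 10.4 and 10.7). Section 10.7 asks for end-of-study assessments after early discontinuation only where they can be done. A patient who stops before Week 3 and misses that visit has a pre-dose sample only. Such a patient cannot show a new antibody but is still in the safety set.

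**Working it through.** **Inputs**
- N = 15, from section 15.2: "The planned total target accrual for this study is 15 subjects".
- Cohort size 3, from the synopsis: "Four cohorts of 3 patients will be treated with different doses of AFM13 and dose regimens".
- ADA counts x are assumptions, because the documents give no expected ADA rate; a range is shown.

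**Method check against the plan's own figure.** Section 15.2 gives an exact 95% interval of 52% to 96% for 12/15. The Clopper-Pearson limits are the 2.5% quantile of Beta(x, n−x+1) and the 97.5% quantile of Beta(x+1, n−x). For x = 12 and n = 15 these are 51.9% and 95.7%, so the stated interval reproduces.

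**What the planned statistics show on 0/1 data.** The mean is p = x/n. The sample SD is √[n·p(1−p)/(n−1)], which depends on p and n alone. For 3/15: √(15 × 0.2 × 0.8 / 14) = √0.1714 = 0.414. For 12/15 the product p(1−p) is the same, so the SD is again 0.414.

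| ADA-positive | Mean | SD | Median | Range | n/N (%) with exact 95% CI |
|---|---|---|---|---|---|
| 0/15 | 0 | 0 | 0 | 0 to 0 | 0% (0 to 21.8%) |
| 1/15 | 0.067 | 0.258 | 0 | 0 to 1 | 6.7% (0.2 to 31.9%) |
| 3/15 | 0.200 | 0.414 | 0 | 0 to 1 | 20.0% (4.3 to 48.1%) |
| 5/15 | 0.333 | 0.488 | 0 | 0 to 1 | 33.3% (11.8 to 61.6%) |
| 7/15 | 0.467 | 0.516 | 0 | 0 to 1 | 46.7% (21.3 to 73.4%) |

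The median and range are the same in every row from 1/15 to 7/15.

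**Zero counts.** With x = 0 the upper limit is 1 − 0.025^(1/n). For n = 15: 1 − 0.025^(1/15) = 21.8%. For one cohort, n = 3: 1 − 0.025^(1/3) = 70.8%. The planned SD is 0 in both cases.

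**Denominator.** Section 15.7.4 restricts the PK analysis to safety-set patients with a baseline and at least one post-baseline measurement. Section 15.9.1 has no matching condition. As an illustration only, suppose 3 of 15 patients had no post-baseline sample. Three positives would then be 3/15 = 20% or 3/12 = 25%, and a zero count would have an upper limit of 21.8% or 1 − 0.025^(1/12) = 26.5%, depending on a choice the plan does not state.

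**The case against.** The case for leaving the text alone has real substance.

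- *The rate is not lost.* A reader might infer that the immunogenicity rate would go unreported. The documents do not support that: the mean of a 0/1 code is the proportion, and all data will be listed, so with about 15 patients the count can be read off. What stands is that the planned summary is badly chosen and carries no measure of uncertainty.
- *Neutralising function may be quantitative.* It is tempting to treat it as yes/no as well. Section 9.1 says only that it will be assayed, and sections 13.9 and 14.14 leave details to the Immunobiology Research Manual, which is not part of the document. If the readout is a titre or per cent inhibition, mean, SD, median and range suit that half of the sentence.
- *Unsampled patients are not said to be negative.* A reader might infer that they would be counted that way. Section 15.9.1 does not say so, and a patient with no result would contribute nothing to a mean. The gap is an unstated denominator, not a demonstrated miscount.
- *Intervals are not the plan's general habit.* Exact intervals are assigned to the response rate (synopsis and section 15.7.1), not to adverse-event incidence or categorical biomarkers. This argues against asking for them in every cohort, where 0/3 gives 0 to 70.8% and conveys almost nothing. One overall interval is a modest request.
- *A SAP is still to be signed before database lock* (section 15.1). It could correct this, but the protocol names a specific method, which a SAP may well carry over.

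**Conclusion.** The point holds as a minor one. Section 15.9.1 names a method that does not fit ADA presence, and no other section supplies the right one. The cost is an uninformative summary: the median and range do not distinguish 6.7% from 46.7%, and an SD of 0 at 0/15 sits beside an exact upper limit of 21.8%. The missing denominator rule is a smaller, separate gap, and its size cannot be judged because the number of patients without a post-baseline sample is unknown.

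This rests on presence being recorded as positive or negative per patient, on N = 15 with all patients sampled (except in the denominator illustration), and on illustrative counts. It does not extend to neutralising function unless that readout proves categorical. The primary analysis and the sample size are unaffected.

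**What to change.** Replace the summary in 15.9.1, and carry the change into the SAP:

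- Report n/N (%) of patients ADA-positive at baseline and newly positive after baseline, by cohort and overall.
- Take N as safety-set patients with a baseline and at least one post-baseline ADA sample, the rule 15.7.4 already uses for PK. State how many treated patients are left out.
- Give an exact 95% interval for the overall rate only.
- Report neutralising function as n/N (%) if the assay result is categorical. Keep mean, SD, median and range for quantitative readouts only.

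This takes a sentence or two of text. It needs no new samples and no change to the sample size.
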